**Investigation of the Effects of Bisphosphonate on the
Gingival Crevicular Fluid Levels of Sclerostin and the
DKK-1 in Individuals with Postmenopausal
Osteoporosis with Periodontal Changes**

Document Date: December, 2018

Uploaded: September, 2020

Study Protocol

Individuals with chronic periodontitis and osteoporosis between 51 and 66 years (mean age: 57.15 ± 4.93) (group A, n=12), 52 to 66 years (mean age: 57.41 ± 4.94) with systemic healthy chronic periodontitis (group B, n=10), between the ages of 50-63 (mean age: 55.64 ± 3.79) periodontally healthy osteoporotic individuals (group C, n=11) and 52-64 years (mean age: 56.55 ± 4.06) periodontal and systemically healthy individuals (group D, n=10) were included in study. 43 postmenopausal women in total were included in the study. This study involved postmenopausal women admitted to the Ondokuz Mayıs University Faculty of Medicine, Department of Endocrinology and Metabolism between 2016 and 2018. The study protocol was approved by Ethical Board of Ondokuz Mayıs University School of Medicine (OMU KAEK 2016/100) and was carried out in accordance with the ethical standards established in the 1964 Declaration of Helsinki, as revised in 2008. Written informed consent was obtained from each subject before enrollment in the study.

Bisphosphonates were started in the patients who were diagnosed with osteoporosis. Individuals smokes, who had received antibiotic treatment in the last 3 months and/or periodontal treatment in the last 6 months were excluded from the study. Following medical

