crevicular fluid (GCF) was collected with the help of periopaper (Periopaper®; Oraflow, New York, NY, USA) from the regions with the deepest pocket depth with periodontal defect, and in healthy groups it was collected by taking the right mandibular molar region as reference. Each time, the volume value of the collected GCF was determined by the Periotron 8000 device. GCF collected paper strips were placed in eppendorf tubes and stored at -80 ° C until biochemical analysis was performed (NUAIRE Ultra-Low Freezer Model no: Nu-6420E). Following the initial sample collection and recording of patient data (medical, periodontal and radiographic), patients were placed under phase 1 periodontal treatment (scaling and root planing), and oral hygiene habits of the patients were corrected and followed up for 1 year. In this period, periodontal treatments, controls and sample collections of the patients in Group A and Group B who completed phase 1 treatment were repeated at the end of 6th month and at the end of the 12th month after the end of the treatment, their clinical changes were recorded. The clinical data and GCF SOST and DKK-1 levels of osteoporosis groups (Group A and C) and non-osteoporotic chronic periodontitis group (Group B) with bisphosphonate were reevaluated in the determined times.

Biochemical Analysis

SOST and DKK-1 levels in gingival crevicular fluid were determined by ELISA (Enzyme-linked immunosorbent assay) kits (SunRed Human DKK1 ELISA Kit, Cat.No:201-12-063, and SunRedHuman SOST ELISA Kit, Cat No: 201-12 -5418) The SOST and DKK1 assay ratios according to the manufacturer's instructions are 0.2-60 ng / mL 0.5-78 ng / mL, respectively. Sensitivity is 0.412 ng / mL for DKK-1 and 0.17 ng / mL for SOST. Color intensity is measured at 450 nm and the results were calculated using standard curves for each kit. GCF SOST and DKK-1 concentrations were obtained by dividing total amount of SOST and DKK1 values by GCF volume (microliter). Concentration values will be presented in ng / mL.

Statistical Analysis

Statistical analysis was performed using SPSS (version 21, SPSS Inc. Chicago, IL, USA) program. The Shapiro-Wilk test was used to show if the data were consistent with the normal distribution. Comparisons of biochemical data between groups were performed with non-parametric Kruskal-Wallis test and $p <0.05$ was considered as statistically significant. In determining the

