difference group, p value was divided by the number of comparison and $p < 0.016$ was accepted as significance level (Mann-Whitney U test with Bonferroni correction). Friedman test was used to determine the time difference in groups and $p < 0.05$ was considered as statistically significant.

3. Armitage GC. Development of a classification system for periodontal diseases and conditions. *Ann Periodontol* 4,1:1-6, 1999.

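### The plan states no between-group test of change in SOST or DKK-1: its only test over time is Friedman within each group, and its between-group tests name neither visit nor quantity

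*Combined protocol and SAP*

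**What the plan says.** The Statistical Analysis section names four procedures. Shapiro-Wilk checks normality. For groups: "Comparisons of biochemical data between groups were performed with non-parametric Kruskal-Wallis test", at 0.05. For locating the differing group by Mann-Whitney: "p value was divided by the number of comparison and $p < 0.016$ was accepted as significance level". For time: "Friedman test was used to determine the time difference in groups and $p < 0.05$ was considered as statistically significant". Nothing else is stated: no change score, baseline-adjusted comparison or group-by-time test.

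The Study Protocol section supplies the setting.
- Drug: "Bisphosphonates were started in the patients who were diagnosed with osteoporosis". That describes Groups A (n=12) and C (n=11). Group B (n=10) is defined as systemically healthy with periodontitis.
- Scaling comes after the first sample: "Following the initial sample collection and recording of patient data", "patients were placed under phase 1 periodontal treatment (scaling and root planing".
- Follow-up is scheduled explicitly for two groups: "sample collections of the patients in Group A and Group B who completed phase 1 treatment were repeated at the end of 6th month", and again at 12 months.
- The closing sentence on follow-up lists Groups A and C, and then: "non-osteoporotic chronic periodontitis group (Group B) with bisphosphonate were reevaluated in the determined times". Re-sampling of Group D is not described.

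**The concern.** Women in A started bisphosphonate and also had scaling and root planing. Both could move SOST and DKK-1 over the year, so a significant Friedman test in A does not say which did. B is scaled and not osteoporotic, so it is the described group against which A's change can be set. The plan never says that this comparison is made.

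Without it, a reader has two substitutes: set the Friedman result in A beside the one in B, or compare follow-up levels. The first is not a test of a difference. The second is a valid test of levels, but it carries forward whatever gap existed at baseline and says nothing by itself about change.

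Three facts needed to read any A-B comparison are also unclear: when bisphosphonate started relative to the first GCF sample, whether Group C was scaled (and from when its visits are counted), and what the phrase attaching bisphosphonate to Group B means.

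**Working it through.** **1. What each stated test can answer**

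| Test | Compares groups? | Uses time? | Visit or quantity stated? |
|---|---|---|---|
| Kruskal-Wallis | yes | not stated | no |
| Mann-Whitney, 0.016 | yes | not stated | no |
| Friedman | no | yes | within each group |

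With three visits, the Friedman statistic for a group of n women is Q = [12/(n·3·4)]·ΣRⱼ² − 3n·4, where Rⱼ is the rank sum of visit j within that group. No other group's data enter it.

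**2. Does the threshold settle the matter?** 0.05/3 = 0.0167, given as 0.016, implies three comparisons. All pairs among four groups would be six: 0.05/6 = 0.0083. Three fits the pairs among A, B and C, the groups followed up. It fits three chosen baseline contrasts equally well. It fixes neither visit nor quantity.

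**3. Reading two Friedman tests side by side.** The documents give no SD or correlation, so these inputs are assumed: normal data, SD 1 at each visit, equal correlation between visits of 0.3, 0.5 or 0.7, all visits complete, and the same true shift in A and B at 6 and 12 months. The group sizes, 12 and 10, are from the plan. There were 20,000 simulated trials per setting. Frequency of A significant and B not:

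| Common shift (SD) | corr. 0.3 | corr. 0.5 | corr. 0.7 |
|---|---|---|---|
| 0 | 5.8% | 5.4% | 5.7% |
| 0.3 | 11.1% | 13.2% | 17.3% |
| 0.5 | 20.0% | 24.3% | 30.8% |
| 0.7 | 28.7% | 32.3% | 29.3% |
| 0.9 | 32.8% | 29.5% | 15.7% |
| 1.2 | 24.3% | 14.0% | 2.8% |
| 1.5 | 10.7% | 3.5% | 0.3% |

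The groups are independent, so this is P(A significant) × [1 − P(B significant)]. As a hand check, with no change and correlation 0.5, a separate run gave 0.059 and 0.046, and 0.059 × 0.954 = 0.056. The rate is highest where each test has middling power.

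A Mann-Whitney test of A versus B on change from baseline, in the same settings, rejects in 4.1-4.6% at 0.05.

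**4. The scale matters.** That 4-5% holds for an equal shift on the scale analysed. Suppose instead that the data are lognormal (correlation 0.5) and both groups fall by the same proportion, 1 log-scale SD. Rejection at 0.05:

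| Baseline A-B gap (log SD) | Absolute change, log SD 0.5 | Absolute change, log SD 1.0 | Log ratio |
|---|---|---|---|
| 1.0 | 11% | 19% | about 4% |
| 1.5 | 21% | 35% | about 4% |

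On the absolute scale, a baseline gap can therefore reappear as an apparent difference in change.

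**5. Power of the added test.** The SD of change is √[2(1 − ρ)], which is 1 at ρ = 0.5. By exact Mann-Whitney (critical U 29 at 0.05 and 26 at 0.025), power for a 1.0 SD difference is about 55% at 0.05 and 46% at 0.025. For 1.5 SD it is about 89% and 83%. Over correlations 0.3-0.7, the 0.025 figures span about 33-70% and 68-97%. The approximate 95% CI half-width at ρ = 0.5 is 2.086 × √(1/12 + 1/10) = 0.89 SD, using t on 20 df.

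**The case against.** The strongest reply is that Kruskal-Wallis and Mann-Whitney on biochemical data could be meant to cover changes, and that the three-way threshold points to the followed groups. That is possible, but the text does not say so, and the point is only about what is stated.

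Next, the harm depends on a reader misusing the Friedman results. That is fair. A reader might infer that the plan adopts significance in A but not in B as its criterion; no section does. The table shows what that reading would cost, not an error rate of the plan. The cost is small when the common change is nil or large.

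A reader might also count significant follow-up levels as false positives. They are not: such a test is right about levels and misleads only if taken as a difference in change.

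A third tempting inference is that Group B received bisphosphonate. B is defined as systemically healthy and the drug is tied to an osteoporosis diagnosis, so the phrase is probably a misplaced modifier, but the two places must be reconciled. Likewise, only A and B are named as completing phase 1 treatment, and C is periodontally healthy, so the likelier reading is that C was not scaled.

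Finally, the gain is limited. A and B differ in osteoporosis as well as drug, and the past tense suggests that the analysis may already be done. Both limits stand. They restrict what can be concluded but do not supply the missing comparison. Choosing A versus B at 12 months is my proposal; the plan ranks no contrast or visit.

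**Conclusion.** The point holds in this form: the plan states no between-group test of change, and the tests it does state cannot, without an unstated step, separate a change in A from the scaling that B also had. It should be fixed. It does not show that any named test is invalid or that a faulty decision rule was adopted.

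Its size depends on assumptions. With equal true change in A and B, separate Friedman tests favour A alone in 5-6% of trials when nothing changes, about 11-33% for a common change of 0.3-0.9 SD, and 0.3-11% at 1.5 SD. These figures rest on normal data, correlation 0.3-0.7 and complete visits, none of which the documents supply. The textual finding needs none of these assumptions.

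**What to change.** 1. Add a Mann-Whitney comparison of A versus B on each woman's change from baseline to 12 months, for SOST and DKK-1, on one scale named in advance. The log ratio is preferable for positive concentrations. Report an estimate with a 95% CI (Hodges-Lehmann would suit). State the multiplicity rule for the two biomarkers: 0.025 each is my suggestion, since the plan corrects only across group comparisons.
2. For Kruskal-Wallis and Mann-Whitney, state the visit and whether levels or changes are used. Draw no between-group conclusion from separate Friedman tests.
3. Reconcile the wording that attaches bisphosphonate to Group B with the statement of who started the drug. From the records, state when the drug started relative to the first GCF sample and whether C was scaled. If the drug came first in some women, say that change from baseline misses part of any effect.
4. Label the test post hoc if the data have already been analysed. Limit conclusions to association, because no untreated osteoporotic group is described.

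The cost is some wording, a records check and a few lines of analysis on samples already described as collected. The drawback is modest power, about 55% for a 1.0 SD difference at 0.05 and 46% at 0.025 (assumed correlation 0.5), so a non-significant result would not show that A and B changed alike.
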